1.1 Title

Full title:

Prevalence of pelvic vein thrombosis in women attending gynaecological outpatient clinics: A prospective observational cross-sectional study Short title:

Prevalence of pelvic vein thrombosis in women

1.3 Protocol Details

Version 3 17th October 2014

2 Signature Page

Prevalence of pelvic vein thrombosis

3 Contents

3.1	Background and literature review	Page: 5
3.2	Aims and Objectives	Page: 7
3.3	Study design	Page: 7
3.4	Study group	Page: 7
3.5	Recruitment of participants	Page: 8
3.6	Data collection	Page: 9
3.7	Data handling	Page: 10
3.8	Study procedure	Page: 11
3.9	Statistical Plan	Page: 14
3.10	Compliance	Page: 14
3.11	Study administration	Page: 15
3.12	Publication plan	Page: 15
3.13	Indemnity statement and Incident reporting	Page: 15
3.14	Appendix	Page: 17

4 Abbreviations

COCP = combined oral contraceptive pill GDOTU = Gynaecology Diagnostics and Outpatient Treatment Unit POP = progestogen only pill VTE = venous thromboembolism DVT = deep vein thrombosis PE = pulmonary embolism TV US = transvaginal ultrasound

5 Summary of Research

Deep vein thrombosis is an important health problem. Recent studies have shown that a proportion of women attending for a gynaecological ultrasound scan have evidence of asymptomatic pelvic vein thrombosis. This is a novel observation and the clinical significance of this finding is unknown. The primary aim of our study is to establish the prevalence of asymptomatic pelvic vein thrombosis in the population of women attending gynaecological outpatient clinics. Our secondary objectives are to study the natural history of pelvic vein thrombosis and to identify factors which may contribute to their formation.

We are planning to conduct a prospective cross sectional observational study. We aim to recruit women who are referred to our gynaecological outpatient department for clinical assessment and ultrasound scans. In all women, in addition to the standard examination of pelvic organs, we will examine the pelvic veins and look for the signs of thrombosis. Those with evidence of blood clots in the pelvis will be offered a thrombophilia screen. Women with positive results will be then referred for haematological assessment. Those with negative thrombophilia screen will be followed up at one, three and six months following the initial diagnosis or until resolution is documented on the scan. Women with persistent clots after six months follow up will also be offered haematological assessment and advice. We aim to include 2574 women over 19 months.

6 Background

6.1 Literature review and justification

Deep venous thrombosis (DVT) affecting lower limbs is a potentially serious medical disorder, which may cause pain and result in venous thromboembolism (VTE). This is more likely to occur in older women and other predisposing factors include prolonged immobility, infection, cancer

and surgery ¹. The risk of VTE is also increased in younger women who are pregnant and in those who are using the combined oral contraceptive pill (COCP). In the UK, pulmonary embolism remains a leading cause of direct maternal death during pregnancy. However, recent enquiry into maternal deaths in pregnancy showed a significant fall in the absolute number of deaths attributed to VTE form 33 in the triennium 2003-2005 to 16 in 2006–2008. This could be a results result of better recognition of at-risk women and more widespread use of thromboprophylaxis. The risk of VTE in women taking COCP has been estimated at 50 - 100/100,000 women years, which represents up to a 10 - fold increase over the background risk². Women with congenital or acquired thrombophilia are also at increased risk of developing VTE³.

Compression ultrasound (CUS) is a standard test for the diagnosis of DVT of the lower limb. The diagnostic technique was developed over 20 years ago⁴ and involves applying gentle pressure on the veins of the limb using the ultrasound probe. Inability to compress a vein indicates the presence of DVT⁵. Other signs of DVT on ultrasound are venous dilatation, intraluminal echogenicity and absence of colour flow signals on Doppler examination⁶. It has been shown that CUS has a sensitivity of 97.5% for the diagnosis of deep vein thrombosis and it has largely superseded contrast venography as the investigation of choice⁷.

Women may also develop isolated pelvic vein thrombosis which is considered to be rare in non – pregnant women ^{8, 9}. It is also unknown whether risks associated with pelvic vein thrombosis are comparable to those with thrombosis affecting lower limbs. The diagnosis of pelvic vein thrombosis is difficult due to non - specific symptoms and is usually made only after the thrombus extends into the veins of the lower limb. Torkzad et al.¹⁰ compared magnetic resonance angiography (MRA) to CUS for the diagnosis of deep – vein thrombosis. In their study, 3 out of 27 symptomatic pregnant women examined had a normal CUS but were found to have ileo-femoral thrombosis when examined within 72 hours by MRA¹⁰.

In recent years an increasing number of women are having transvaginal ultrasound scans for a wide range of gynaecological indications. The pelvic veins are often examined in women presenting with pelvic pain to rule out pelvic congestion syndrome. However, there is a paucity of data on the diagnosis and prevalence of incidental pelvic vein thrombosis in women. Recently we have published a first report in the literature describing ultrasound diagnosis of pelvic vein thrombosis in six asymptomatic non-pregnant women. Our data showed that pelvic vein thrombosis is not as rare as previously thought and that majority of women had identifiable predisposing factors for development of blood clots. Although the diagnosis of pelvic vein

6

thrombosis on ultrasound is relatively simple the natural history, clinical significance and optimum management strategy are unknown.

7 Aims and Objectives

The primary aim of the study is to determine the prevalence of pelvic vein thrombosis in women attending gynaecology outpatient clinic. The secondary outcomes are: natural history and identification of factors contributing to clot formation.

8 Study Design

8.1 Design Summary

This will be a prospective observational cross-sectional study.

9 Study Group

Women referred for gynaecological assessment who consent to take a part in the study will be the subjects.

Our population will be sourced from the following referral pathways:

- GP
- Internal hospital referrals

9.1 Centres participating

 Gynaecology Diagnostic and Outpatient Treatment Unit, Elizabeth Garrett Anderson Wing, University College Hospital

9.2 Inclusion Criteria

• Women aged 18 and over attending gynaecology outpatient clinics

- Signed written consent
- Ability to tolerate transvaginal scan
- Women found to have a pelvic vein clot on transvaginal scan

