9.4 Eligibility

All women booked for pelvic ultrasound examination will be sent a study information sheet with their appointment letter. Those who meet the inclusion criteria and provide written consent will be recruited into the study.

10 Recruitment of Participants

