10.1 Method of recruitment

Patients will be recruited at the time of attendance at the gynaecology outpatient clinic. All women referred to the gynaecological outpatient clinic will have a patient information leaflet sent with their appointment letter. At their gynaecology appointment, those women who have read the study information and meet the inclusion criteria will be asked to sign a consent form prior to the scan (see Appendix). Patients will be informed that there will no personal identifiable details recorded if they are recruited. Those women who do not wish to take part in the study will have their transvaginal scan as per routine practice and their care will be unaffected.

Hospital trust translators are used if there is a language barrier as standard practice. The patient's GP will be notified of the findings and participation into the study if the participant consents to this.

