14.1 Sample Size Determination and Power

We aim to screen 2574 eligible participants over 2 years. The prevalence of this condition is unknown but our initial experience indicates that it may be around 5/1000 women and the sample size has been calculated on this proportion ⁽¹⁷⁾.

14.2 Statistical Methods:

We will perform multivariate logistic regression analysis to identify factors which may be contributing to asymptomatic pelvic vein thrombosis.

15 Compliance

15.1 Subject Compliance:

Patients who do not have a pelvic vein thrombus will not be followed up in the study. Those with a thrombus will have scheduled follow up appointments at one, three and six, months. If there is evidence of clot resolution at the first or second visit, no further follow up will be arranged. Women who fail to attend for their appointments, will be contacted by telephone and will be offered another date for the follow up visit.

15.2 Withdrawal of subjects:

Patients will have the opportunity to withdraw from the study at any point in the study period. Patients will be asked if the data collected upto the point of withdrawal can be used in the final analysis.

16 Study Administration

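### Section 9.2 lists a pelvic vein clot on the scan as an inclusion criterion, so the primary outcome is written as a condition of entry, against the rest of the protocol

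*Protocol*

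**What the plan says.** Section 9.2 of the protocol gives one list of four inclusion criteria. The first three are age and clinic attendance, written consent, and being able to tolerate the scan. The fourth is "Women found to have a pelvic vein clot on transvaginal scan". No ‘or’, sub-heading or note restricts it to a later stage of the study. Section 9.4 makes the list operative: "Those who meet the inclusion criteria and provide written consent will be recruited into the study".

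Other sections describe a different population:

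- Section 7 (aims): "The primary aim of the study is to determine the prevalence of pelvic vein thrombosis in women attending gynaecology outpatient clinic".
- Section 5 (summary): the pelvic veins are examined in every woman, and "We aim to include 2574 women over 19 months".
- Section 9 (study group): the subjects are referred women who consent. No clot is required.
- Section 10.1 (recruitment): women who have read the information and "meet the inclusion criteria will be asked to sign a consent form prior to the scan".
- Section 14.1 (sample size): "We aim to screen 2574 eligible participants over 2 years", with an expected prevalence of about 5 per 1000.
- Section 14.2 (methods): "We will perform multivariate logistic regression analysis to identify factors which may be contributing to asymptomatic pelvic vein thrombosis".
- Section 15.1 (compliance): "Patients who do not have a pelvic vein thrombus will not be followed up in the study".

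**The concern.** A prevalence is the number of women with the condition divided by the number examined. The denominator must therefore be settled without regard to the scan result. The fourth bullet of 9.2 makes the result part of eligibility, so the stated entry rule removes the clot-free women who form nearly all of the denominator. They are also the comparison group for the risk-factor model, because a logistic regression needs women with and without the outcome.

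The eligibility section is where one looks to see who is enrolled and counted. If it disagrees with the aims, the recruitment procedure and the sample size, the protocol does not give a single answer to what the primary estimate is a proportion of.

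**Working it through.** **Inputs.** N = 2574 women (Sections 5 and 14.1); p = 5/1000 = 0.005 (Section 14.1).

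**The plan's own sample size.** The usual formula for estimating one proportion is n = z² p(1 − p)/d². Section 14.1 gives p but neither the precision d nor the confidence level, so 2574 cannot be reproduced exactly. Assuming 95% confidence, N = 2574 implies d = 1.96 × √(0.005 × 0.995/2574) = 0.0027. Rounded choices bracket the figure: d = 0.0027 gives 2622 and d = 0.00275 gives 2528. Nothing below depends on d. What matters is that the calculation takes 0.5% as the expected proportion, which makes sense only if almost all the women counted are clot-free.

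**Section 9.2 against the other sections.**

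1. *Timing (10.1).* The criteria are to be met and consent signed before the scan. Clot status is unknown then, so the fourth criterion cannot be checked when eligibility is decided. Strictly applied, no woman could be enrolled.
2. *Population (5 and 9).* All consenting referred women are subjects and all have their veins examined. Section 9.2 would admit only those with a clot.
3. *Sample size (14.1).* The 2574 are called eligible. If eligibility required a clot, the expected proportion among them would be 100%, not 0.5%.
4. *Clot-free women (15.1).* The sentence on patients without a thrombus is ambiguous alone. Read with Sections 5 and 9, it treats them as study patients who have no further visits.

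**Section 9.2 applied literally.** Every participant is a case, so prevalence = x/x = 100% whatever x is. With 13 women, the exact 95% lower limit is 0.025^(1/13) = 0.753, giving an interval of 75% to 100% against a planning value of 0.5%. The regression outcome takes one value only, so no odds ratio can be estimated.

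**Scale of the mismatch.** Finding 2574 women with a clot at p = 0.005 would take 2574/0.005 = 514,800 scans, which is 200 times the planned intake. This shows that the literal reading is not what was planned. It does not measure an error in the study's result.

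**The evident intent.** Expected cases = 2574 × 0.005 = 12.87, about 13 (95% binomial range 6 to 20). Non-cases = 2574 − 13 = 2561. With 13 cases, prevalence = 13/2574 = 0.51%, exact 95% interval 0.27% to 0.86%. Prevalence can be estimated, and both outcome classes are present for the regression.

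**The case against.** The strongest reply is that nobody could run the study as 9.2 reads. Consent precedes the scan, so the result cannot control entry, and the sections set out above point consistently to all scanned women. The bullet is most naturally a misplaced note on who goes on to follow-up. That stands. It makes this a wording contradiction and not a choice of design, and under the evident intent the bullet changes no estimate.

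A reader might go further and infer that the investigators planned a cases-only study, or that the reported prevalence will be biased upwards because records are kept mainly for women with clots. The documents support neither. The aim and the sample size exclude the first. On the second, this is a single centre (9.1, 16.1), and Section 11 has history and scan findings, including whether a clot is present, recorded at the initial consultation as part of usual care. Only the follow-up scans depend on a thrombus. Nothing in the text suggests that clot-free records would be dropped.

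The reply does not remove the need for a correction. Section 9.4 refers to the list in 9.2 without qualification. Reading the bullet as an alternative route into the study would not help either, since it would admit women on the outcome itself.

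**Conclusion.** The point holds as an internal contradiction in the eligibility criteria. As written, Section 9.2 with 9.4 makes the primary outcome a condition of entry, and this cannot be squared with Sections 5, 7, 9, 10.1 and 14.1, or with 15.1 read alongside them. On the literal text, prevalence is 100% by construction and the risk-factor model cannot be fitted. On the intended reading, about 13 cases and 2561 non-cases are expected among 2574 women. These counts rest on the protocol's own assumption of 5 per 1000.

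It does not follow that the study cannot meet its aims, or that its result is wrong by any stated amount. The defect lies in the rule that defines the denominator. It should be corrected because that rule governs the primary estimate. How well about 13 events would support a multivariable model is a separate question.

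**What to change.** Delete the fourth bullet from Section 9.2. State that the prevalence denominator and the regression sample are every consented woman whose pelvic veins are scanned, whatever the result. This brings 9.2 into line with Sections 5, 9, 10.1 and 14.1. It is a short wording amendment and changes neither recruitment, scanning, nor the planned analyses.

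If clot presence is to be kept as the condition for entering follow-up, put it in the follow-up section. That step takes more than one line, because the protocol disagrees with itself on who is followed: Sections 5 and 13.3 schedule repeat scans for women with a negative thrombophilia screen, while 15.1 schedules them for all women with a thrombus. Those passages must be reconciled by the investigators before a follow-up group is defined. The deletion in 9.2 need not wait for that.

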9.3 Exclusion Criteria

- Inability to tolerate transvaginal scan
- Severe pelvic pain

9.4 Eligibility

All women booked for pelvic ultrasound examination will be sent a study information sheet with their appointment letter. Those who meet the inclusion criteria and provide written consent will be recruited into the study.

10 Recruitment of Participants

10.1 Method of recruitment

Patients will be recruited at the time of attendance at the gynaecology outpatient clinic. All women referred to the gynaecological outpatient clinic will have a patient information leaflet sent with their appointment letter. At their gynaecology appointment, those women who have read the study information and meet the inclusion criteria will be asked to sign a consent form prior to the scan (see Appendix). Patients will be informed that there will no personal identifiable details recorded if they are recruited. Those women who do not wish to take part in the study will have their transvaginal scan as per routine practice and their care will be unaffected.

Hospital trust translators are used if there is a language barrier as standard practice. The patient's GP will be notified of the findings and participation into the study if the participant consents to this.

10.2 Subject Stipends or Payments

None

10.3 Study Timetable

Recruitment will run between the 1st January 2015 to 31st August 2016.

8

Sept 2014, ver 3.

11 Data Collection

The data source will be from the history taken and ultrasound scan performed during the consultation, which is recorded onto a secure NHS database (Viewpoint). Although this is usual standard care, the clinical data will be included as part of the research study. Information about the ultrasound findings will be collected at the initial consultation and at the follow up scan appointments if there is a pelvic vein thrombus at four weeks, three months and six months by the student involved in this study ([name], EGA wing, UCLH).

The following data will be collected at the time of consultation and scan: anonymous demographic information (age, BMI, ethnicity, smoking history); obstetric history (gravida, parity, pregnancy outcome, type of delivery, uterine instrumentation in pregnancy, instrumentation of uterus outside pregnancy); gynaecological history (age of menarche, number of days of menstruation, menorrhagia, dysmenorrhea, dyschezia, breastfeeding history, use of COCP or POP, use of coils); past medical history (cancer, varicose veins, recent surgery); ultrasound findings (uterine shape/anomaly, presence of adenomyosis, presence of fibroids/mass and size, ovarian volume, adnexal mass, maximum uterine vein diameter, blood flow velocity, flow rate, presence of clot, size of clot at initial scan and then at follow up at one, three and six months); thrombophilia screening results. Please see appendix 20.3 for a full data set.

The data will be entered into a spreadsheet (Microsoft Excel version 14.0) (see appendix 20.3).

12 Data Handling and Record Keeping

12.1 Confidentiality and Security

All patient records will be handled according to NHS confidentiality practices. Patient identifiable data will not leave NHS hospital premises. Anonymised hard copies of patient clinical letters will be placed in a dedicated file which will be kept in a locked cabinet in the clinic office.

12.2 Data transfer

Anonymous clinical data will be collected from patients in accordance with the patient consent, patient information sheet and section 11 of this protocol. The anonymous clinical data will be available to [name] (student) and [name] (Chief Investigator) for statistical

analysis. [name] will act as the data controller of such data for the study. [name] will process, store and dispose of the anonymous demographic data, ultrasound findings and thrombophilia results in accordance with all applicable legal and regulatory requirements, including the Data Protection Act 1998 and any amendments thereto. All data information will be anonymised and stored on encrypted NHS drives.

12.3 Intellectual Property Rights

All background intellectual property rights (including licenses) and know-how used in connection with the study shall remain the property of the party introducing the same and the exercise of such rights for purposes of the study shall not infringe any third party's rights.

All intellectual property rights and know-how in the protocol and in the results arising directly from the study, but excluding all improvements thereto or clinical procedures developed or used by each participating site shall belong to UCL.

Nothing in this section shall be construed so as to prevent or hinder the participating site from using know-how gained during the performance of the study in the furtherance of its normal activities of providing or commissioning clinical services, teaching and research to the extent that such use does not result in the disclosure or misuse of confidential information or the infringement of an intellectual property right of UCL. This does not permit the disclosure of any of the results of the study, all of which remain confidential.

12.4 Archiving

Any data generated during the study in non-identifiable format may be retained indefinitely by the student. All identifiable data will be purged at the end of the research.

13 Study Procedures

13.1 History taking

The first step of the study will be to obtain a full history from the patient. This is part of routine clinical practice for all patients who present to the gynaecology outpatient clinic. The information elicited from the history that will be included has been referred to in section 11 (see appendix 20.3). 10 Sept 2014, ver 3.

13.2 Procedure for transvaginal ultrasound

13.2.1 Routine transvaginal ultrasound of pelvic organs

Women referred to our gynaecology clinic at University College Hospital are assessed by gynaecologists trained in transvaginal ultrasonography. Before the examination, a full history is taken and entered in a secure NHS clinical database (Viewpoint). All women with symptoms of gynaecological disease undergo a transvaginal scan as part of a routine assessment. The examination is performed systematically in the following manner: first the uterus is examined in the transverse plane to identify the cervical canal, the uterine cavity and both interstitial portions of the fallopian tubes. Acquired uterine anomalies, such as fibroids or adenomyosis, are diagnosed based on direct visualization using previously described diagnostic criteria^{12,13}. Once the examination of the uterus is completed, the ovaries and the adnexae are also examined. The presence of any abnormalities in the ovaries or the adnexa is documented. If a significant abnormality, such as suspected neoplasm, is detected a senior member of the team is asked to repeat the examination to confirm the findings.

